## PROTOCOL SYNOPSIS

**TITLE:** A MULTICENTER, RANDOMIZED, DOUBLE-BLIND, ACTIVE (OSELTAMIVIR)-CONTROLLED STUDY TO ASSESS THE SAFETY, PHARMACOKINETICS, AND EFFICACY OF BALOXAVIR MARBOXIL IN OTHERWISE HEALTHY PEDIATRIC PATIENTS 1 TO < 12 YEARS OF AGE WITH INFLUENZA-LIKE SYMPTOMS

**PROTOCOL NUMBER:** CP40563

**VERSION NUMBER:** 1

**IND NUMBER:** 126653

**EudraCT NUMBER:** 2018-002169-21

**TEST PRODUCT:** Baloxavir marboxil (RO7191686)

**PHASE:** III

**INDICATION:** Influenza

**SPONSOR:** F. Hoffmann-La Roche Ltd

### **Objectives and Endpoints**

This study will evaluate the safety, pharmacokinetics, and efficacy of baloxavir marboxil compared with oseltamivir in a single influenza episode in otherwise healthy pediatric patients (i.e., 1 to < 12 years of age) with influenza-like symptoms. Specific objectives and corresponding endpoints for the study are outlined below.

Safety (Primary) Objective	Corresponding Endpoints

 
• To compare the safety of a single dose of baloxavir marboxil with 5 days of oseltamivir administered twice daily
 
	
 
• Incidence, severity, and timing of adverse events, serious adverse events, vital sign measurements, and clinical laboratory test results
 

Pharmacokinetic Objective	Corresponding Endpoints

 
• To evaluate the PK of baloxavir marboxil after single-dose administration
 
	
 
• Plasma concentrations of baloxavir marboxil (pro-drug) and S-033447 (active metabolite) will be summarized by time (C24 and C72) and body weight
 
• Population PK model derived parameters (e.g., AUCinf, Cmax, Tmax, t1/2) (modelling report)
 

Efficacy (Secondary) Objectives	Key Corresponding Secondary Endpoint

 
• To evaluate the clinical efficacy of baloxavir marboxil compared with oseltamivir
 
	
 
• Time to alleviation of influenza signs and symptoms, defined as the length of time taken from the start of treatment to the point at which all of the following criteria are met and remain so for at least 21.5 hours:               
 
– A score of 0 (no problem) or 1 (minor problem) for cough and nasal symptoms (items 14 and 15 of the CARIFS)
 
– A “yes” response to the following question on the CARIFS: “Since the last assessment has
 
 
 

	
the subject been able to return to day care/school, or resume his or her normal daily activity in the same way as performed prior to developing the flu?"
 
 
– First return to afebrile state (tympanic temperature <math>\leq 37.2^{\circ}\text{C}</math>)
 

Efficacy (Secondary) Objectives	Corresponding Endpoints

 
• To evaluate the clinical efficacy of baloxavir marboxil compared with oseltamivir
 
	
 
• Duration of fever (time to return to afebrile state [tympanic temperature <math>\leq 37.2^{\circ}\text{C}</math>] and remaining so for at least 21.5 hours)
 
• Duration of symptoms (alleviation of all symptoms as defined by a score of 0 [no problem] or 1 [minor problem] and remaining so for at least 21.5 hours, for all 18 symptoms specified in the CARIFS questionnaire)
 
• Time to return to normal health and activity
 
• Frequency of influenza-related complications (death, hospitalization, radiologically confirmed pneumonia, bronchitis, sinusitis, otitis media, encephalitis/encephalopathy, febrile seizures, myositis)
 
• Proportion of patients requiring antibiotics
 

Secondary Virology Objective	Corresponding Endpoints

 
• To evaluate the virological activity of baloxavir marboxil compared with oseltamivir
 
	
 
• Time to cessation of viral shedding by virus titer and by RT-PCR
 
• Change from baseline in influenza virus titer and in the amount of virus RNA (RT-PCR) at each time point
 
• Proportion of patients with positive influenza virus titer and proportion of patients positive by RT-PCR at each time point
 
• Area under the curve in virus titer and in the amount of virus RNA (RT-PCR)
 

Exploratory Objectives	Corresponding Endpoints

 
• To evaluate the polymorphic and treatment-emergent amino acid substitutions in the PA, PB1, and PB2 genes and drug susceptibility in patients with evaluable virus
 
• To evaluate extended PK parameters of baloxavir marboxil after single-dose administration
 
	
 
• Polymorphic and treatment-emergent amino acid substitutions in the PA, PB1, and PB2 genes
 
• Drug susceptibility in patients with evaluable virus
 
• Non-compartmental PK parameters (intensive PK)
 

AUCinf= area under the concentration–time curve from Time 0 to infinity; C24= plasma concentration 24 hours postdose (acceptable time window: 20 to 28 hours); C72= plasma concentration 72 hours postdose; CARIFS= Canadian Acute Respiratory Illness and Flu Scale; Cmax= maximum plasma concentration; PA= polymerase acidic protein; PK= pharmacokinetic; RT-PCR= reverse transcriptase-polymerase chain reaction; t1/2= half-life; Tmax= time to maximum plasma concentration.

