## Appendix 1 Schedule of Activities

Day(s)	Treatment Period						Follow-Up Period				
	D1		D2	D3	D4	D5	D6	D7-9	D10	D15	D29 or ET
Visits	V1 Screening	V1 Post-dose	V2	OpV1 a	V3		V4		V5	OpV2 a	V6
Visit Window (days)					+1		±1		±2	±3	±3
Written informed consent/assent	x										
Inclusion/exclusion criteria	x										
Demographics	x										
Medical history b	x										
Randomization	x										
Study drug administration c		x	x	x	x	x					
Patient diary:											
Body temperature measurement d	Four times daily				Twice daily			Once daily			
Assessment of influenza symptoms e	Twice daily							Once daily			
Physical examination	x f		x f	(x) f	x f		x		x	(x g )	x f
Vital signs measurement	x		x	(x)	x		x		x	(x g )	x h
Adverse event assessment		x	x	(x)	x		x		x	(x g )	x
Concomitant therapies assessment	x		x	(x)	x		x		x	(x g )	x
Interview for meal consumption	x	x									
Clinical laboratory tests		x					x			(x g )	(x g )
Nasal/nasopharyngeal swabs (virology test) i	x		x		x		x		x	(x g )	(x g )

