## Appendix 1 Schedule of Activities (cont.)

Day(s)	Treatment Period					Follow-Up Period					
	D1	D2	D3	D4	D5	D6	D7-9	D10	D15	D29 or ET	
Visits	V1 Screening	V1 Post-dose	V2	OpV1 a	V3		V4		V5	OpV2 a	V6
Sparse PK samples j		x	(x) j		(x) j		x j				
Intensive PK samples k		x	x		x		x k				

CARIFS= Canadian Acute Respiratory Illness and Flu Scale; D=Day; ET=early termination; OpV=optional visit; PK=pharmacokinetic; V=visit.

- a OpV1 and OpV2 are optional visits to be performed at the discretion of the investigator or parent/caregiver, for example, to obtain intensive PK analyses, or in the event of persistent influenza symptoms.
- b Prior therapies will also be reviewed.
- c Oseltamivir and matching placebo will be given orally, 12 hours apart. If the first dose is taken after 4 pm (16:00 hours) on Day 1, the next dose will be taken in the morning of Day 2. For these patients, the 10th dose will be taken on the morning of study Day 6. If the first dose is taken prior to 4 pm (16:00 hours) on Day 1, the next dose should be taken in the evening of the same day (i.e., prior to midnight on the same calendar day with a minimum of 7 hours between doses). For these patients, the 10th dose will be taken in the evening of study Day 5.
- d The parent/caregiver will assess and record in the patient diary, body temperature (tympanic assessment) four times daily (morning, noon, evening, and bedtime) from Days 1 to 3; twice daily (morning and evening) on Days 4 to 9; once daily on Days 10 to 15.
- e The parent/caregiver will complete the CARIFS questionnaire twice daily (morning and evening) on Days 1 to 9 and then once daily on Days 10 to 15.
- f Body weight and height will be measured on Days 1 and 29, only. Physical examinations on Days 2, 3, and 4 will be limited symptom-directed physical examinations and may be performed by a mobile nursing professional.
- g Conduct assessment if the investigator determines that influenza symptoms or viral shedding are persisting or at the investigator's discretion.
- h Vital signs will be recorded if abnormal physical examination findings or adverse events are recorded since last visit or at investigator's discretion on Day 29.
- i At least two nasal and/or nasopharyngeal swabs (one for each nostril) to be taken at each visit.

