## **4.6.2 Virology (Secondary) Endpoints**

### **Time to cessation of viral shedding by virus titer**

Time to cessation of viral shedding by virus titer is defined as the time, in hours, between the initiation of any study treatment and first time when the influenza virus titer is below the limit of detection. Patients whose virus titers have not reached the limit by the last observation time point will be treated as censored at that time point. One day is converted into 24 hours.

Patients with a positive virus titer on Day 1 will be included in this analysis.

This endpoint will be summarized using descriptive statistics by treatment, as well as Kaplan-Meier plots.

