### **Time to cessation of viral shedding by RT-PCR**

Time to cessation of viral shedding by RT-PCR, in hours, is defined as the time between the initiation of any study treatment and first time when the virus RNA by RT-PCR is below the limit of detection. Patients whose virus RNA have not reached the limit by the last observation time point will be treated as censored at that time point. For the patients with multiple virus types, this endpoint is defined as the time between the initiation of the study treatment and first time when the virus RNA by RT-PCR is below the limit of detection for all virus types. One day is converted into 24 hours.

Patients with a positive virus RNA on Day 1 will be included in this analysis.

This endpoint will be summarized using descriptive statistics by treatment, as well as Kaplan-Meier plots.

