### **Area under the curve in the amount of virus RNA (RT-PCR)**

AUC in virus RNA (RT-PCR) will be presented by treatment group and is defined as AUC of change from baseline in the amount of virus RNA (RT-PCR) from Day 1 to Day 10. AUC is calculated using the trapezoidal method similar to AUC in virus titer. Patients with a positive RT-PCR result on Day 1 will be subjected to this analysis. The lower limit of quantification is defined as  $2.18$  for flu A and  $2.93$  for flu B ( $\log_{10}$  virus particles/mL). If a patient is infected with multiple virus types, the sum of those the amount of virus RNA will be used for analysis.

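### Viral shedding time has no common end of follow-up, so its Kaplan-Meier tail after Day 10 can depend on selectively taken swabs

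*Protocol*

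**What the plan says.** The Protocol synopsis and Table 1 list "Time to cessation of viral shedding by virus titer and by RT-PCR" as a secondary virology endpoint. SAP Section 4.6.2 dates the event, for titer, at the "first time when the influenza virus titer is below the limit of detection", and words the RNA event in the same way. The censoring rules are "Patients whose virus titers have not reached the limit by the last observation time point will be treated as censored at that time point" for titer and "Patients whose virus RNA have not reached the limit by the last observation time point will be treated as censored at that time point" for RNA. Neither names an end day. Both endpoints are reported by arm with Kaplan-Meier plots and descriptive statistics, and SAP Section 4.6.4 repeats them by virus type and subtype.

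In Protocol Appendix 1 (repeated in SAP Appendix 2) swabs are unconditional on Days 1, 2, 4, 6 and 10. On Day 15, itself an optional visit, and on Day 29 or early termination they are bracketed under footnote g: "Conduct assessment if the investigator determines that influenza symptoms or viral shedding are persisting or at the investigator's discretion". SAP Table 2 has analysis windows for Days 13 to 22 and for Day 23 onwards, so these swabs enter the analysis.

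Most sibling endpoints in SAP Section 4.6.2 stop at Day 10. Change from baseline and proportion positive use Days 2, 4, 6 and 10, for both titer and RNA. The RNA area under the curve is "AUC of change from baseline in the amount of virus RNA (RT-PCR) from Day 1 to Day 10". The titer area under the curve states no end day.

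**The concern.** Kaplan-Meier estimation assumes that a child censored at a given time would go on to clear like those still followed. Take two children who are both RNA positive at Day 10. One is well, has no further swab and is censored there. The other is still ill, is swabbed again, and stays at risk until about Day 15 or Day 29. The second child then stands in for both. If persistence of illness is related to persistence of virus, the assumption fails because of how the follow-up is arranged. The degree of failure may also differ by arm, since treatment can affect persistence.

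At stake are the part of each curve after Day 10 and any median that falls there. The plots and medians are the reported result, and the SAP plans no sensitivity analysis behind them. The subtype subgroups would have still fewer children at risk after Day 10.

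**Working it through.** **Plan's own figure.** The documents give none for this endpoint. The only design figure is the adverse-event table: 1 − (1 − p)^80 for p = 1% to 5% gives 55.2, 80.1, 91.3, 96.2 and 98.3%, as printed. It has no bearing here.

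**Time scale.** Hours = (day − 1) × 24, so Day 10 = 216 h, Day 15 = 336 h and Day 29 = 672 h.

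**Children at risk after Day 10.** Expected number = arm size × share PCR-confirmed × p10 × q. Here p10 is the share still positive at Day 10 and q is the share of those swabbed later. Arm sizes of 80 and 40 are from the Protocol. The other inputs are assumptions, with 80% confirmed (64 and 32 children):

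| p10 | q | Baloxavir | Oseltamivir |
|---|---|---|---|
| 5% | 30% | 1.0 | 0.5 |
| 20% | 30% | 3.8 | 1.9 |
| 40% | 30% | 7.7 | 3.8 |
| 60% | 10–50% | 3.8–19.2 | 1.9–9.6 |

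**When the tail is biased.** Let c_s and c_u be the proportions clearing between Day 10 and Day 15 among swabbed and unswabbed children.

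- Kaplan-Meier estimate at Day 15: p10 × (1 − c_s)
- True value: p10 × [1 − q·c_s − (1 − q)·c_u]
- Difference: p10 × (1 − q) × (c_u − c_s)

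With p10 = 0.40, q = 0.30, c_s = 0.40 and c_u = 0.80, the estimate is 0.24 and the truth is 0.40 × 0.32 = 0.13, a difference of 0.11. If c_s = c_u the difference is zero. If swabbed children cleared faster, the sign would reverse.

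**Illustration on a continuous scale.** Assumptions: RNA clearance time is log-normal with log-SD 0.5 and correlates 0.6 with symptom persistence; only the 5 to 15% most persistently ill are swabbed at Day 15; arms are 64 and 32. The true share still shedding at time t is 1 − Φ[ln(t / median) / 0.5].

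| RNA median | True share, Day 10 | True share, Day 15 | Kaplan-Meier, Day 15 |
|---|---|---|---|
| 240 h | 0.58 | 0.25 | about 0.39–0.48 |
| 200 h | 0.44 | 0.15 | 0.24–0.32 |
| 120 h | 0.12 | 0.02 | 0.03–0.07 |

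The ranges span both arm sizes and both swabbing shares. Where no child in a simulated arm was swabbed, the curve was carried flat. Leaving such arms out lowers the 120 h range to about 0.03–0.04.

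**When the median is touched.** Data after Day 10 set the median only if more than half of an arm is still positive at 216 h. In the adult and adolescent study (Protocol Section 1.2.2) the titer medians were 24 h on baloxavir and 72 h on oseltamivir, far below that. No RNA clearance time is given for any study.

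**Effect of a Day 10 cut-off.** In a separate simulation with exponential clearance, a true median of 5 days and arms of 32, the Day 10 share was 0.29 with the cut-off, 0.28 with selective later swabs and 0.29 with later swabs in all. These agree to within simulation noise.

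**The case against.** The strongest reply is that little depends on this. Safety is primary, virology is secondary and descriptive, and no test or error rate is involved. The proportions positive on Days 2, 4, 6 and 10 already show each arm's position at Day 10, and everything up to that visit is unaffected. All of this stands, and it limits the point to the tail and possibly one median.

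Three stronger readings are tempting but unsupported:

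- **That the curve beyond 216 h is biased as a matter of fact.** Footnote g also allows swabs for persisting shedding or at pure discretion. If every child still positive at Day 10 were swabbed, or if swabbed and unswabbed children cleared alike, there would be no bias. Nor must the numbers be tiny: the table above reaches about 19 baloxavir children.
- **That the RT-PCR median is wrong because RNA falls more slowly than titer.** The earlier paediatric study's Day 2 changes (−1.75 for RNA, −4.20 for titer, both log10) are in virus particles/mL and TCID50/mL, from different assays. They do not show when RNA falls below its detection limit.
- **That the titer endpoint is compromised to the same degree.** Earlier medians of 24 h and 72 h make its median very probably safe, although those patients were not young children.

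It can also be said that truncation is one choice among several. A Day 10 sensitivity analysis with numbers at risk would keep the planned curve. That is a workable second best, but the main figure would still carry the selected tail.

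**Conclusion.** The concern holds in a conditional form. The SAP sets no common end of follow-up, the schedule makes swabs after Day 10 depend on judged persistence or discretion, and the analysis windows admit them. The Kaplan-Meier tail can therefore be outcome-dependent, and it may rest on few children. Whether it is biased, and in which direction, depends on whether swabbed children clear at a different rate from unswabbed ones.

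Under the assumed inputs the error at Day 15 ranges from about 0.01 to 0.05 in absolute terms (120 h median) to about 0.14 to 0.23 (240 h median). The RT-PCR median is exposed only in the slow-clearance case, which the documents neither show nor exclude. The point merits a change because the remedy is cheap and matches how most sibling endpoints are already defined.

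**What to change.** In SAP Section 4.6.2, for both shedding-time endpoints, and in the shedding subgroups of Section 4.6.4, state that a child without cessation is censored at the Visit 5 (Day 10) swab, or at the last unconditional scheduled swab if that is earlier. This also settles that the last observation means a swab. Add numbers at risk to the plots, report by arm the share not ceased at Day 10, state that the median was not reached by Day 10 where that applies, and list Day 15 and Day 29 swabs separately.

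The cost is a short SAP edit and no new data. Later swabs leave the main curve and the median may be unavailable: with exponential clearance and a true median of 10 days, it was not reached in 69% of simulated arms of 64 and 60% of arms of 32. Censoring times will still vary somewhat, because the Visit 5 window runs from Day 8 to Day 12 (168 to 264 h), but every child is due that swab regardless of illness.

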## **Study Design**

### **Description of Study**

This is a multicenter, randomized, double-blind, active-controlled (i.e., oseltamivir) study to assess the safety, pharmacokinetics, and efficacy of baloxavir marboxil compared with oseltamivir in pediatric patients 1 to < 12 years of age with influenza-like symptoms.

The approved dose for oseltamivir in pediatric patients 1 to 12 years of age is twice daily (BID) for 5 days, based on body weight. Baloxavir marboxil will be given as a single-dose, based on body weight at screening. Either drug, along with the corresponding placebo of its comparator in this trial, will be started at the time of randomization.

Patients will be screened and randomized on Day 1 and assigned in a 2:1 ratio to receive a single oral dose of baloxavir marboxil based on body weight (2 mg/kg for patients weighing < 20 kg or 40 mg for patients weighing  $\geq$  20 kg) or oseltamivir (dose based on body weight) for 5 days. Re-screening of patients who fail to meet the inclusion and exclusion criteria will not be permitted for the same illness episode.

The study consists of two periods: a 5-day treatment period (mandatory visits on Days 1, 2, and 4) and a 24-day safety follow-up period (mandatory visits on Days 6, 10, and 29). Therefore, the total study duration for each patient will be 29 days.

During the 5-day treatment period, each patient randomized to baloxavir marboxil will receive the oseltamivir matching placebo BID for 5 days, and those patients randomized to oseltamivir will receive one dose of baloxavir marboxil matching placebo on Day 1.

The following assessments will be conducted at clinic visits: physical examination, vital signs, adverse events, concomitant therapies, clinical laboratory tests, and nasal/throat swabs.

Throughout the treatment and safety follow-up periods, the parents/caregivers will maintain a patient diary for each patient in order to record body temperatures (tympanic assessment), influenza symptoms, and acetaminophen use. Temperatures will be recorded four times daily (morning, noon, evening, and bedtime) on Days 1 to 3; BID (morning and evening) on Days 4 to 9; and once daily on Days 10 to 15. Influenza symptoms will be recorded BID (morning and evening) on Days 1 to 9 and once daily on Days 10 to 15.

This study will be conducted at sites in the United States and globally.

To facilitate early and close monitoring of safety parameters over time, an Internal Monitoring Committee (IMC) will review aggregate safety data on an ongoing basis as defined in the IMC charter. If there is any concern noted in the safety parameters, the Sponsor may suspend or discontinue a treatment arm or the entire study, as appropriate.

### **Number of Patients**

This study is designed to enroll approximately 120 otherwise healthy male and female pediatric patients with influenza-like symptoms presenting within 48 hours of symptom onset.

Patients will be recruited in parallel to the following two cohorts:

- 5 to < 12 years of age (minimum 40 patients)
- 1 to < 5 years of age (minimum 20 patients)

### **Target Population**

#### **Inclusion Criteria**

Patients must meet the following criteria for study entry:

- Written informed consent/assent for study participation obtained from patient's parents or legal guardian, with assent as appropriate by the patient, depending on the patient's level of understanding
- Aged 1 to < 12 years at randomization (Day 1)
- Parent/guardian willing and able to comply with study requirements, in the investigator's judgment
- Patient able to comply with study requirements, depending on the patient's level of understanding
- Patient with a diagnosis of influenza virus infection confirmed by the presence of all of the following:

- Fever  $\geq 38^{\circ}\text{C}$  (tympanic temperature) at screening
- At least one respiratory symptom (either cough or nasal congestion)
- The time interval between the onset of symptoms and screening is  $\leq 48$  hours (the onset of symptoms is defined as the time when body temperature first exceeded  $37.5^{\circ}\text{C}$  if known, or the time when the first symptom was noticed by patient, parent or caregiver)

#### Exclusion Criteria

Patients who meet any of the following criteria will be excluded from study entry:

- Severe symptoms of influenza virus infection requiring inpatient treatment
- Concurrent infections requiring systemic antiviral therapy at screening
- Require, in the opinion of the investigator, any of the prohibited medication during the study
- Previous treatment with peramivir, laninamivir, oseltamivir, zanamivir, or amantadine within 2 weeks prior to screening
- Immunization with a live/attenuated influenza vaccine in the 2 weeks prior to randomization
- Concomitant treatment with steroids or other immuno-suppressant therapy
- Known HIV infection or other immunosuppressive disorder
- Uncontrolled renal, vascular, neurologic, or metabolic disease (e.g., diabetes, thyroid disorders, adrenal disease), hepatitis, cirrhosis, or pulmonary disease or patients with known chronic renal failure
- Active cancer at any site
- History of organ transplantation
- Known allergy to either study drug (i.e., baloxavir marboxil and oseltamivir) or to acetaminophen
- Females who have commenced menarche (i.e., child-bearing potential)
- Participation in a clinical trial within 4 weeks or 5 half-lives of exposure to an investigational drug prior to screening, whichever is longer

